A Different Approach to Preventing Thrombosis (ADAPT): A Randomized Controlled Trial Comparing Low Molecular Weight Heparin to Acetylsalicylic Acid in Orthopedic Trauma Patients

Study Protocol and Statistical Analysis Plan

NCT02774265

7/26/18

Study Design

ADAPT was a single-center randomized controlled trial that compared safety of low molecular weight heparin (LMWH) versus aspirin with respect to bleeding and wound complications in orthopaedic trauma patients within 90-days of their fracture. Ethics approval was obtained by the University of Maryland Institutional Review Board and informed consent was obtained for all enrolled patients.

Eligibility Criteria

All adult trauma patients (age \geq 18 years) with operative extremity fracture proximal to the carpals/metatarsals or any hip or acetabular fracture requiring VTE prophylaxis were included in the study. We excluded prisoners, pregnant patients, non-English speaking patients, patients with an indication for therapeutic anticoagulation or high dose aspirin (greater than 81mg daily) and patients receiving pre-existing confounding prophylaxis or therapeutic anticoagulation prior to admission or greater than two doses of prophylaxis in our hospital prior to consent. Patients with recent VTE within the last 6 months, impaired creatinine clearance, history of heparin-induced thrombocytopenia or aspirin or non-steroidal anti-inflammatory allergy or another contraindication to receiving one of the study medications were also excluded.

Randomization and masking

Patients were randomly assigned venous thromboembolism prophylaxis by LMWH or aspirin using block randomization (6 per block) with the assistance of the trial's REDCap system by research staff at the study site after enrollment. Surgeons and patients were not masked to the treatment groups.

Intervention and Procedures

Patients allocated to the LMWH group received two 30mg BID doses daily with allowance for dose adjustment based on BMI or Xa levels. Patients allocated to the aspirin group received 81mg doses, twice daily. The duration of prophylaxis was at the treating surgeon's discretion, with no minimum or maximum duration. Mechanical prophylaxis with intermittent pneumatic compression devices is also ordered as part of clinical protocol for all inpatients. Study follow-up was conducted at 3-months post-fracture either at the patient's clinic appointment or over the phone. A chart review was also conducted at this time.

All prophylaxis doses were monitored daily during the index admission by the study's research staff. Additionally, outpatient adherence was assessed at all clinical follow-up visits. Any contamination or unplanned crossover was closely monitored.

Outcomes

The primary endpoint was bleeding complications within 90-days from the date of injury. Bleeding complications included a 2g/dL or greater drop in hemoglobin, blood transfusion, gastro-intestinal (GI) bleeding, surgical site hematoma requiring reoperation, or other bleeding events requiring intervention or resulting in death. Secondary exploratory outcomes included wound complications defined as a deep surgical site infections (SSI) based on the Centers for Disease Control and Prevention criteria that required operation, and VTE (including massive, sub-massive, or clinically significant pulmonary embolism and clinically significant deep vein thrombosis (either distal or proximal)). No screening of asymptomatic patients for VTE events was done. All adverse events were reported to the IRB as per local requirements. Two medical monitors reviewed the safety of the trial and all serious adverse events.

Statistical Analysis

The study's sample size calculations were based on a retrospective review of the study centers database, which determined a 1-year historic bleeding complication rate of 15% in the study population. Based on arthroplasty literature, we hypothesized that aspirin would be associated with a 5% absolute reduction bleeding complications. Using a one-sided Fisher's Exact sample size calculation, an alpha of 0.05, and an allocation ratio of 1:1, a sample of 1150 patients would provide 80% power. This target sample was inflated to 1380 to allow for up to 20% loss to follow up. Within a year of starting the trial, funding was obtained to commence a large pragmatic trial comparing these two interventions with a primary endpoint of pulmonary embolism-related death. This trial was subsequently stopped after the enrollment of 329 participants, for which the safety of these two interventions was assessed

Analysis followed the intention-to-treat principle and included all patients in the groups to which they were randomly assigned. Bivariable analysis and multivariable logistic regression model were used to assess the association between type of VTE prophylaxis and the primary and secondary endpoints. The treatment effects were reported as odds ratios (OR) and 95% confidence intervals (CI). The analyses adjust for the time each patient is at risk of the analyzed study event, to a maximum of 90 days. Patients who did not complete the 90-day follow up were deemed at risk from their time of enrollment until their last documented follow-up. Kaplan-Meier curves were used to plot the time to study events by treatment arm.

Patient crossover and contamination was assessed at several thresholds including $\geq 5\%$, $\geq 10\%$, $\geq 25\%$, $\geq 50\%$ of the patient's total study doses being the non-allocated prophylaxis medication. All thresholds were assessed in a secondary as-treated analysis. A threshold of more than 50% of the patient's total study doses being the non-allocated prophylaxis medication is presented for the as-treated analysis in the results. Factors associated with patient crossover in this study sample were also assessed.

At the completion of the trial, we investigated possible effect measure modification by patient smoking status, history of VTE, mechanism of injury (high energy versus low energy), fracture location (upper extremity versus lower extremity), fracture severity (open fracture versus closed fracture), and non-orthopaedic injury (abdomen, head, or chest) determined by an Abbreviated Injury Scale score of ≥ 2 . Each variable was added into the primary analysis as an interaction term. Statistically significant interactions were then analyzed stratifying by the effect measure modifier. The treatment effects in the stratified analysis were reported as odds ratios (OR) and 95% confidence intervals (CI), adjusting for time at risk.

All analyses were performed using JMP Pro Version 13 (SAS Institute, Cary, NC). This study was registered with ClinicalTrials.gov (NCT02774265).

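### The target of 1380 is 1150 × 1.20, so it keeps 1150 patients only up to 16.7% loss to follow-up, not the stated 20% (minor)

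*Combined protocol and SAP*

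**What the plan says.** The sample-size paragraph of the Statistical Analysis section builds the target in two steps.

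- **Evaluable number.** The centre's own database "determined a 1-year historic bleeding complication rate of 15% in the study population", and the planned effect is stated as "we hypothesized that aspirin would be associated with a 5% absolute reduction bleeding complications". The method is given as "Using a one-sided Fisher's Exact sample size calculation", with alpha 0.05 and equal allocation. The result is that "a sample of 1150 patients would provide 80% power".
- **Allowance for loss.** "This target sample was inflated to 1380 to allow for up to 20% loss to follow up".

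The same paragraph reports that a larger trial of the two treatments was then funded, and that "This trial was subsequently stopped after the enrollment of 329 participants".

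Two other places bear on what a lost patient means. Under Intervention and Procedures, the 3-month follow-up is by clinic visit or telephone, and "A chart review was also conducted at this time". In the analysis text, patients with incomplete 90-day follow-up "were deemed at risk from their time of enrollment until their last documented follow-up". No other part of the document gives a different inflation rule.

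**The concern.** Multiplying the evaluable number by 1 + d is a common shortcut for a loss fraction d, but it falls short. Losses are taken from the larger enrolled number, so the correct step is to divide by 1 − d. The plan's figure matches the shortcut exactly, and the tolerance it states is therefore larger than the one its figures deliver.

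What is at stake is the description of the planned design. A reader would conclude that the trial, fully enrolled, could lose one patient in five and still have the stated 80% power. The planned 1150 sits almost exactly on 80%, so there is no slack to absorb a shortfall.

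**Working it through.** **Inputs, all from the Statistical Analysis section:** event rates 15% (LMWH, historic) and 15% − 5% = 10% (aspirin); one-sided Fisher's exact test; alpha 0.05; 1:1 allocation; 1150 patients for 80% power; 20% loss; target 1380.

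**1. Reproduce the evaluable number.** Exact enumeration of the one-sided Fisher test with 575 per arm gives power 0.8003. As a cross-check, the continuity-corrected one-sided formula gives 580 per arm, 1160 in total, close to 1150. The base number is sound.

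**2. Reproduce the inflated number.**
- N × (1 + d) = 1150 × 1.20 = 1380, which is the plan's figure exactly.
- N / (1 − d) = 1150 / 0.80 = 1437.5, rounded up to 1438.
- Difference: 1438 − 1380 = 58 patients, about 4%.

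**3. Find the loss that 1380 can absorb.**
- 1380 − 1150 = 230 patients.
- 230 / 1380 = 16.7%.

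**4. See what 20% loss leaves.**
- 0.20 × 1380 = 276 lost.
- 1380 − 276 = 1104 remaining, which is 1150 − 1104 = 46 short.

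**5. Power on the planning test.** Exact enumeration, one-sided Fisher, alpha 0.05, 15% versus 10%. The unequal splits are assumptions, chosen only to show sensitivity; the documents give no loss rate by arm. Each starts from 690 per arm and has the same 276 losses in total.

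| Scenario | LMWH / aspirin analysed | Power |
|---|---|---|
| 1150 patients, as planned | 575 / 575 | 80.0% |
| 20% loss, equal between arms | 552 / 552 | 78.4% |
| 15% lost on LMWH, 25% on aspirin | 586 / 518 | 78.3% |
| 25% lost on LMWH, 15% on aspirin | 518 / 586 | 78.5% |
| 10% lost on LMWH, 30% on aspirin | 621 / 483 | 77.7% |
| 30% lost on LMWH, 10% on aspirin | 483 / 621 | 78.1% |
| Every lost patient's outcome recovered | 690 / 690 | 86.3% |

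All rows but the first and last assume that lost patients contribute no data. At equal loss the drop is 80.0 − 78.4 = 1.6 percentage points.

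**6. Place this against what happened.** 329 / 1380 = 23.8% of the target was enrolled.

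**The case against.** Four points can be made for the plan.

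*The denominator is not stated.* If 20% means 20% of the 1150, then 230 extra patients replace 230 losses and 1380 is consistent. This is possible but weak. A loss rate is ordinarily a share of those enrolled, and the sentence speaks of loss, not of over-enrolment. If the sponsor meant the latter, the wording still needs to say so.

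*Lost patients are not dropped.* The analysis keeps all randomised patients in their assigned groups, counts incomplete patients up to their last contact, and is supported by a chart review at 3 months. So 1104 need not be the number analysed, and 78.4% is the figure at equal 20% loss when nothing is recovered. This stands as a limit on the size of the effect, and the 86.3% row shows the other end. The documents do not say how many outcomes would be recovered. It does not rescue the sentence: inflating the sample at all presupposes that lost patients would not count towards the 1150.

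*The effect is tiny and nothing depends on it.* Both parts are true. A change of 1.6 points is small beside the uncertainty in round planning inputs, and the trial ended at 329 participants for an unrelated reason. This is why the point is minor.

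*Rewriting the tolerance changes the record.* The planners did state 20%, and replacing it with 16.7% records a tolerance they did not choose. This is a fair reason to prefer a correction that leaves the 20% in place and states what it would have left.

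**Conclusion.** The concern holds, as a minor error. Taking loss as a share of patients enrolled, 1380 preserves the planned 1150 up to 16.7% loss and not up to 20%; a 20% allowance would have needed 1438. At 20% loss the planning-test power is 78.4% rather than 80.0%, provided loss is equal between arms and lost patients give no data. The assumed unequal splits run from 77.7% to 78.5%.

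These power figures belong to the planning test alone. They do not describe the logistic regression adjusted for time at risk that the plan uses for its analysis. No result from the 329 participants is affected. Confidence in the arithmetic is high.

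**What to change.** Keep 1380 as the historical target and correct the stated tolerance in the sample-size paragraph. Either wording would do:

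- *The target of 1380 allows for up to 16.7% loss to follow-up while keeping 1150 patients.*
- *With 20% loss, the target of 1380 would leave 1104 patients and about 78% power on the planning test, if loss is equal between arms and lost patients contribute no data.*

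The second, added as a note beside the existing sentence, keeps the planners' stated 20% on record. The cost is one sentence; no analysis or result changes.

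### With 329 patients, unqualified logistic regression for VTE, deep infection and the history-of-VTE interaction has no stated provision for sparse or empty cells; penalized likelihood would be safer

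*Combined protocol and SAP*

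**What the plan says.** The Statistical Analysis section names a single modelling approach for bleeding and for both secondary outcomes: "Bivariable analysis and multivariable logistic regression model were used to assess the association between type of VTE prophylaxis and the primary and secondary endpoints". Effects are given as odds ratios with 95% confidence intervals. The only adjustment it specifies is follow-up time: "The analyses adjust for the time each patient is at risk of the analyzed study event, to a maximum of 90 days". Kaplan-Meier curves are mentioned as plots.

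The Outcomes section labels the secondary outcomes exploratory and defines them narrowly: deep surgical site infection that needed an operation, and clinically significant pulmonary embolism or deep vein thrombosis. Asymptomatic patients were not screened for VTE.

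For effect modification, history of VTE is one of six factors examined for bleeding: "Each variable was added into the primary analysis as an interaction term". Interactions found significant are then stratified. Under Eligibility Criteria, the excluded groups include "Patients with recent VTE within the last 6 months" and patients who have an indication for therapeutic anticoagulation.

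On numbers, the sample size paragraph calculates 1150 patients, inflated to 1380, and then reports: "This trial was subsequently stopped after the enrollment of 329 participants".

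The documents do not give an expected VTE or deep-infection rate, the prevalence of past VTE, a covariate list beyond time at risk, the estimator or interval type, or a rule for zero cells or non-convergence.

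**The concern.** Maximum-likelihood logistic regression has no finite treatment odds ratio when one arm has no events. The fitted log-odds ratio drifts towards infinity, and a Wald interval or p-value taken from it carries no information. The same happens to an interaction term when one history-by-arm cell contains no bleed. Even when every cell has an event, a handful of events gives estimates that are unstable and biased away from the null.

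VTE is the outcome against which any bleeding advantage of aspirin has to be weighed, so an extreme or missing odds ratio there is unhelpful even in an exploratory analysis. For the interactions, the plan uses statistical significance to decide which factors are stratified. With an empty cell, that decision could rest on an uninformative p-value.

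**Working it through.** **Inputs from the documents.** 329 patients, 1:1 allocation (taken as 165 LMWH and 164 aspirin); bleeding 15% with a hypothesized 5-point reduction on aspirin, so 15% and 10%; one-sided Fisher's exact test at 0.05; 1150 patients for 80% power.

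**Assumed, because the documents give no figure.** VTE or deep-infection rate 1 to 5%, equal in both arms; prevalence of past VTE 2 to 15%.

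**The plan's own figure.** Exact power of the one-sided Fisher test at 575 per arm, 15% versus 10%, is 80.03%, so 1150 is reproduced. It is sized on bleeding alone.

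**1. VTE and deep infection: chance that at least one arm has no events.** With rate r, let a = (1 − r)^165 and b = (1 − r)^164. The chance is a + b − ab.

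| Assumed rate | Expected events (329 × r) | a | b | At least one empty arm |
|---|---|---|---|---|
| 1% | 3.3 | 0.190 | 0.192 | 35% |
| 2% | 6.6 | 0.036 | 0.036 | 7% |
| 3% | 9.9 | 0.0066 | 0.0068 | 1.3% |
| 5% | 16.4 | 0.0002 | 0.0002 | 0.04% |

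If the full 20% loss allowed for in the plan removed those patients altogether (132 and 131 left), the chances at 1%, 2% and 3% become 46%, 14% and 3.6%. At the intended 575 per arm and a 1% rate, the chance was 0.6%, so the early stop accounts for most of the exposure.

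**2. History-of-VTE interaction on bleeding: chance that a history-by-arm cell has no bleed.** With prevalence q, the chance of no patient in an arm having both past VTE and a bleed is A = (1 − 0.15q)^165 for LMWH and B = (1 − 0.10q)^164 for aspirin. At least one such cell: A + B − AB.

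| Assumed prevalence | Patients with past VTE | A | B | At least one cell without a bleed | Same, bleeding 30% in both arms |
|---|---|---|---|---|---|
| 2% | 6.6 | 0.609 | 0.720 | 89% | 61% |
| 5% | 16.4 | 0.289 | 0.440 | 60% | 16% |
| 10% | 32.9 | 0.083 | 0.192 | 26% | 1.3% |
| 15% | 49.4 | 0.023 | 0.084 | 11% | 0.1% |

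The last column replaces 0.15 and 0.10 by 0.30. It tests sensitivity to the observed bleeding rate being higher than planned.

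**3. Main bleeding comparison.** Expected bleeds are 165 × 0.15 for LMWH plus 164 × 0.10 for aspirin, or 41 in all. The chance of an empty arm is 0.85^165 plus 0.90^164, below 1 in 10 million.

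**4. What failure looks like.** Take assumed counts of 4/165 versus 0/164. An ordinary logistic fit gives log-odds ratios of 7.9, 17.9 and 22.9 after 10, 20 and 25 iterations, with standard errors of about 15, 2283 and 27809: it does not converge. Without covariates, the Firth estimate equals adding 0.5 to each cell: odds of 4.5 to 161.5 against 0.5 to 164.5, that is 0.0279 against 0.00304, a ratio of 9.2. The reciprocals of the four adjusted counts sum to 2.234, so the standard error of the log is √2.234 = 1.49, giving a Wald 95% interval of about 0.5 to 172. This is finite and shows how little the data say. The Wald interval is used here only for hand calculation.

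**The case against.** The strongest reply is that the alarming figures depend on rates the documents do not supply. That stands for VTE and deep infection. Nothing in the text favours the low end: VTE includes distal as well as proximal thrombosis, and the population includes operative hip, acetabular and open fractures. At 3% or more an empty arm is improbable.

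The interaction figures depend on an unstated prevalence and on the planning bleeding rates. A reader might infer from the exclusions that few patients with past VTE remained. The documents do not say so: VTE more than six months earlier is not excluded as such. At 10% prevalence and 30% bleeding, the chance of a cell without a bleed falls to 1.3%.

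Maximum likelihood is also inferred, from silence. The section names neither estimator nor interval, so it cannot be said that a failing method was specified. Nor can a very low ratio of events to model terms be claimed by counting the six effect modifiers as covariates: they enter as interaction terms, and time at risk is the only named adjustment.

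The secondary outcomes are exploratory, and bivariable analysis and Kaplan-Meier plots sit alongside the model, so the comparison does not rest on one odds ratio. If Wald tests were used, an interaction with an empty cell would have a huge standard error and would probably not reach stratification. That limits one harm, but a non-significant result obtained this way says nothing about whether the effect differs.

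Finally, penalization cannot supply missing events, as the interval of 0.5 to 172 shows. This is correct. The gain is a finite estimate with a usable interval, not precision.

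**Conclusion.** The concern holds in a limited form. If logistic regression means maximum likelihood, 329 patients leave the VTE and deep-infection models exposed to a non-existent odds ratio at event rates of about 2% or less (7% chance at 2%, 35% at 1%). At 3 to 5%, they are exposed to instability from about 10 to 16 events. The history-of-VTE interaction is the weakest point: 89% to 11% over prevalences of 2 to 15% at the planning bleeding rates, and 61% to 0.1% if bleeding were 30% in both arms.

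These results rest on equal event rates in both arms for VTE and deep infection, past VTE being equally common in both arms and unrelated to bleeding, and near-equal allocation.

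Two stronger conclusions are tempting. One is that the VTE comparison will fail or be uninterpretable; with no event rate in the documents, only a conditional risk can be stated. The other is that the trial's bleeding result is undermined; about 41 expected events rule out this particular problem there. Since the affected analyses are exploratory and the remedy is cheap, this is an improvement that should be made rather than a defect in the primary analysis.

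**What to change.** For VTE, deep infection and the interaction models, specify Firth penalized logistic regression with profile-likelihood 95% intervals. Keep treatment and the stated time-at-risk adjustment, and add no further covariates to the VTE and deep-infection models. Falling back to a treatment-only model when events are few would discard the follow-up adjustment that the plan requires, so it is not recommended.

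Report event counts by arm for each secondary outcome. Where a history-by-arm cell has no events, show the counts and do not interpret the interaction p-value. If such a cell has no patients at all, penalization cannot help and only counts can be shown.

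The section is written in the past tense, after enrolment stopped, so this means a wording change and a short reanalysis of existing data; if a penalized or exact method was in fact used, saying so answers the point. The statistical cost is slight shrinkage of the estimates, and the intervals will still be wide because the events are few.

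### The odds ratios adjust for time at risk without saying when that time ends for a patient who bleeds; event-ended time used as a covariate would cost power and, with unequal loss, bias the result

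*Combined protocol and SAP*

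**What the plan says.** The Statistical Analysis section names the model: "Bivariable analysis and multivariable logistic regression model were used to assess the association between type of VTE prophylaxis and the primary and secondary endpoints". Effects are reported as ORs with 95% confidence intervals. The time adjustment follows: "The analyses adjust for the time each patient is at risk of the analyzed study event, to a maximum of 90 days". The only rule for the clock covers incomplete follow-up: "Patients who did not complete the 90-day follow up were deemed at risk from their time of enrollment until their last documented follow-up". The effect-modification analyses repeat the adjustment: "The treatment effects in the stratified analysis were reported as odds ratios (OR) and 95% confidence intervals (CI), adjusting for time at risk". Survival methods appear only as a display: "Kaplan-Meier curves were used to plot the time to study events by treatment arm".

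Under Outcomes, the endpoint window has a different origin from the clock: "The primary endpoint was bleeding complications within 90-days from the date of injury". The composite contains events that can recur: "Bleeding complications included a 2g/dL or greater drop in hemoglobin, blood transfusion".

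Two things are not stated: when time at risk ends for a patient who bleeds, and whether time is a covariate, an offset or something else.

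**The concern.** Time at risk of a particular event ordinarily ends when that event occurs. The Kaplan-Meier curves need exactly that variable, so it should already be in the dataset. If it is also entered as a covariate in the logistic model, the model conditions on something the outcome determines. Every event-free completer has 90 days and every bleeder has fewer. The only event-free patients with short times are dropouts, so the treatment OR comes to depend heavily on the ratio of bleeders to dropouts in each arm. A difference in dropout is then read as a treatment effect.

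The adjustment applies to the primary, secondary and stratified ORs. A reader cannot tell from the text whether those ORs come from a sound model or from this one.

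**Working it through.** **Inputs.** From the Statistical Analysis section: 15% bleeding on LMWH; a 5-point reduction, so 10% on aspirin; 329 enrolled; 1:1 allocation, taken as 165/164; planning allowance of up to 20% loss. Loss by arm, its timing and the timing of bleeding are not in the documents, so they are assumed and varied.

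**The plan's own figure.** One-sided Fisher's exact power at 575 per arm, alpha 0.05, 15% against 10%, is 0.8003. The stated 1150 for 80% power reproduces.

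**Target.** True OR = (0.10/0.90)/(0.15/0.85) = 0.111/0.176 = 0.63.

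**Readings of the clock.** Let E be the event time and L the last follow-up, capped at 90 days. The model is logit P(bleed) = b0 + b1·aspirin + b2·T, and the OR is exp(b1).
- A, event-ended: T = min(E, L).
- B, the non-completer rule taken literally: T = L for non-completers even if they bled; T = min(E, 90) for completers.
- C, follow-up time: T = L whether or not the patient bled.

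**No loss.** Under A and B every bleeder has T < 90 and every non-bleeder has T = 90. Time separates the outcome completely and no finite OR exists (500 of 500 runs). This is a limiting case, since the plan provides for non-completers.

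**Mechanism by hand (reading A).** Take bleeding and loss times uniform over 0–90 days, so half of the bleeds in patients who are lost occur before loss and are seen. Assume 20% loss on LMWH and 10% on aspirin.
- LMWH: observed bleeders = 132 × 0.15 + 33 × 0.15/2 = 22.3; event-free dropouts = 33 − 2.5 = 30.5; odds of bleeding among short-time patients = 0.73.
- Aspirin: observed bleeders = 147.6 × 0.10 + 16.4 × 0.10/2 = 15.6; event-free dropouts = 16.4 − 0.8 = 15.6; odds = 1.00.
- OR among short-time patients = 1.00/0.73 = 1.37.
- Crude OR, ignoring time = (15.58/148.42)/(22.275/142.725) = 0.67.

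With 20% loss in both arms, aspirin has 14.8 bleeders and 31.2 event-free dropouts, odds 0.47, and the short-time OR is 0.47/0.73 = 0.65, close to the truth. Most of the distortion therefore comes from conditioning on time, not from the loss itself. A fitted linear time term also draws on full-time patients and falls between the crude and short-time values.

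**Simulation.** 2,000 runs per scenario, two-sided Wald tests at 5%, median ORs. Bleeding times are early (truncated exponential, mean 10 days), intermediate (mean 30) or uniform. Loss is uniform over 0–90 days. Cells give early / intermediate / uniform.

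| Loss %, LMWH/aspirin | A: event-ended | B: only completing bleeders stop |
|---|---|---|
| 20/20 | 0.63 / 0.63 / 0.62 | 0.62 / 0.62 / 0.63 |
| 20/17 | 0.77 / 0.73 / 0.71 | 0.72 / 0.71 / 0.70 |
| 20/15 | 0.84 / 0.80 / 0.76 | 0.75 / 0.76 / 0.74 |
| 20/10 | 1.33 / 1.16 / 0.97 | 1.00 / 1.02 / 0.92 |
| 10/20 | 0.29 / 0.33 / 0.39 | 0.37 / 0.37 / 0.41 |
| 10/5 | 1.29 / 1.08 / 0.90 | 1.06 / 0.98 / 0.87 |

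- Power under A at 20/20: 12/17/21%, against 27/26/24% without time.
- Null rejection under A: 4–7% at 20/20, 6–8% at 20/17, 8–9% at 20/15, 20–24% at 20/10. Under B: 5–8% at 20/17, 7–8% at 20/15, 13–18% at 20/10.
- Reading C: OR 0.61–0.65 and null rejection 3–6% throughout.
- Log-time offset in place of a covariate: OR 0.55–0.63, null rejection 5.5–10.7%.

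A separate 600-run repeat of reading A gave power of 11/17/20% against 28/28/24% at 20/20, and ORs of 0.75–0.84 at 20/15 and 0.98–1.27 at 20/10.

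**Timing of loss.** With loss only from day 14 at 20/10, A gives 1.31/1.14/1.00 and B gives 0.94/0.98/0.93. With loss only from day 42 and early bleeding, B at 20/10 gives OR 0.61, null OR 1.06–1.08 and null rejection near 4%: the bias is essentially gone, though power is about 5%. With uniform bleeding B still gives 0.90. In the early-bleeding, day-42 setting A often had no stable fit.

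**The case against.** The bias needs three things the documents do not show: a clock that ends at the event, time entered as a covariate, and unequal loss. Without the first, the problem disappears. A log-time offset leaves only mild error. Equal loss leaves a precision cost and almost no bias.

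The one written rule can also be read as follow-up time, because it takes non-completers to their last contact with no exception for bleeders. Recurrent components in the composite fit that reading too. The Kaplan-Meier curves show that event dates exist, not that event-ended time entered the logistic model.

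Follow-up may also have been fairly complete. "All prophylaxis doses were monitored daily during the index admission", and the Intervention and Procedures section provides for 3-month contact in clinic or by phone, plus a chart review. Chart review could also reveal bleeds after the last contact, which the simulations treat as unseen.

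All of this stands, and it makes the bias conditional. It does not close the gap. The event-specific wording remains the more natural reading, and nothing in the text excludes it. Less loss overall is not protection in itself: at 10/5 the event-ended OR is still 0.90–1.29. Under that reading, power is lost even when the arms lose patients equally.

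The difference in clock start (injury or enrollment) has no simulated consequence here. It is a wording point and adds nothing to the bias argument.

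**Conclusion.** The specification gap is certain; the bias is conditional. If time ends at the event and is a covariate, power at an assumed 20/20 loss is about 11–21% instead of 24–28%. A true OR of 0.63 becomes about 0.75–0.84 at 20/15, 1.0–1.3 at 20/10 and 0.3–0.4 at 10/20. If only completing bleeders stop at the event, the bias is smaller and depends on when loss occurs. If time is follow-up not ended by the event, there is no problem.

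These figures rest on assumed loss splits and on assumed timing of loss and bleeding. They take the plan's 15%, a 1-year historic rate, as the 90-day risk, as its own sample size does.

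A reader might infer that the trial's ORs are wrong, or that aspirin's effect was reversed. The documents support neither. They do not show which clock was used, and 20% is a planning allowance, not observed loss. Open-label treatment makes unequal loss possible, not established. ORs clearly above 1 arise here only where one arm loses twice as many patients as the other, and the largest need early bleeding. Nor can one say that the literal non-completer rule always leaves bias, since late loss with early bleeding removes nearly all of it.

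This should be fixed, with moderate confidence: it affects every reported OR, and the correction uses dates already held.

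**What to change.** 1. State that event-ended time at risk is not a covariate in any logistic model, whether primary, secondary or stratified.
2. If the OR is kept, either adjust for follow-up time not ended by the event, capped at 90 days, or omit time. Say which, and in what form time enters.
3. Use one clock start for all patients, reconciling injury (Outcomes) with enrollment (Statistical Analysis).
4. Report one censoring-aware estimate from the dates behind the Kaplan-Meier curves: a Cox hazard ratio, or the 90-day Kaplan-Meier risk difference with 95% CI. In the same simulations the risk difference averaged −4.8 to −5.2 points (true −5) with null rejection 4–6%, and the hazard ratio was 0.63–0.67 with null rejection 3–6%.
5. Report loss to follow-up by arm, so that readers can judge the exposure.

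**Cost.** SAP wording, a re-run and one added effect measure. Omitting time counts dropouts as non-events and leaves a small bias under unequal loss (OR 0.59–0.67 for a true 0.63). With non-event-ended follow-up time, the time coefficient could not be estimated in up to 6% of runs when either arm lost 20%, and up to 19% at 10/5, because no dropout bled; the treatment OR stays finite. If the sponsor already used that clock, one sentence saying so settles the bias question.
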